5.7 Participant withdrawal From Study

A participant must be withdrawn from the study if the participant or the participant's legally acceptable representative withdraws consent from the study.

If a participant withdraws from the study, they will no longer receive study intervention or be followed at scheduled protocol visits.

Specified details regarding procedures to be performed at the time of withdrawal from the study as well as specific details regarding withdrawal from future biomedical research are outlined in Sections 7.1.4.1 and 7.1.4.2.

Discontinuation of Study Therapy after CR

Discontinuation of treatment may be considered for subjects who have attained a confirmed CR that have been treated for at least 24 weeks with pembrolizumab or the combination and had at least two treatments with pembrolizumab beyond the date when the initial CR was declared.

5.8 Participant Replacement Strategy

We anticipate enrollment of 48 patients for which tumor and toxicity assessments following pembrolizumab/olaparib administration can be made. We will replace patients enrolled for which clinical trial discontinuation was performed prior to any administration of pembrolizumab or those for which pembrolizumab is discontinued due to acute hypersensitivity reactions during the first administration of pembrolizumab. An attempt will be made to assess tumor response in all enrolled patients as specified in the protocol. Patients experiencing clinical deterioration after two doses of pembrolizumab, will be considered treatment failures, will count as tumor progression, and will not be replaced.

5.9 Clinical Criteria for Early Trial Termination

Early trial termination will be the result of the criteria specified below:

1. Quality or quantity of data recording is inaccurate or incomplete
2. Poor adherence to protocol and regulatory requirements
3. Incidence or severity of adverse drug reaction in this or other studies indicates a potential health hazard to participants
4. Plans to modify or discontinue the development of the study drug

In the event of Merck decision to no longer supply either study drug, adequate notification will be provided so that appropriate adjustments to participant treatment can be made.

6.0 TRIAL ASSESSMENTS AND PROCEDURES

6.1 Trial Procedures

- Study procedures and their timing are summarized in The Trial Flow Chart - Section 6.0.

- Adherence to the study design requirements, including those specified in the Trial Flow Chart, is essential and required for study conduct.
- The investigator is responsible for ensuring that procedures are conducted by appropriately qualified (by education, training, and experience) staff.
- All screening evaluations must be completed and reviewed to confirm that potential participants meet all eligibility criteria.
- Additional evaluations/testing may be deemed necessary by the investigator, the Sponsor and/or Merck for reasons related to participant safety. In some cases, such evaluation/testing may be potentially sensitive in nature (eg, HIV, Hepatitis C), and thus local regulations may require that additional informed consent be obtained from the participant. In these cases, such evaluations/testing will be performed in accordance with those regulations.

6.1.1 Administrative and General Procedures

6.1.1.1 Informed Consent

The Investigator must obtain documented consent from each potential participant or each participant's legally acceptable representative prior to participating in a clinical trial. If there are changes to a participant's status during the study (e.g. health requirements) the investigator must ensure appropriate consent is in place.

6.1.1.2 General Informed Consent

Consent must be documented by the participant's dated signature or by the participant's legally acceptable representative's dated signature on a consent form along with the dated signature of the person conducting the consent discussion.

A copy of the signed and dated consent form should be given to the participant before participation in the trial.

The initial informed consent form, any subsequent revised written informed consent form and any written information provided to the participant must receive the IRB/ERC's approval/favorable opinion in advance of use. The participant or his/her legally acceptable representative should be informed in a timely manner if new information becomes available that may be relevant to the participant's willingness to continue participation in the trial. The communication of this information will be provided and documented via a revised consent form or addendum to the original consent form that captures the participant's dated signature or by the participant's legally acceptable representative's dated signature.

Specifics about a trial and the trial population will be added to the consent form template at the protocol level.

The informed consent will adhere to IRB requirements, applicable laws and regulations and Sponsor requirements.

6.1.1.3 Inclusion/Exclusion Criteria

All inclusion and exclusion criteria will be reviewed by the investigator or qualified designee to ensure that the participant qualifies for the trial.

6.1.1.4 Medical History

A medical history will be obtained by the investigator or qualified designee. Medical history will include all active conditions, and any condition diagnosed within the prior 10 years that are considered clinically significant by the Investigator. Details regarding the disease for which the participant has enrolled in this study will be recorded separately and not listed as medical history.

6.1.1.5 Prior and Concomitant Medications Review

6.1.1.5.1 Prior Medications

The investigator or qualified designee will review prior medication use, including any protocol-specified washout requirement, and record prior medication taken by the participant within 28 days before starting the trial. Treatment for the disease for which the participant has enrolled in this study will be recorded separately and not listed as a prior medication.

6.1.1.5.2 Concomitant Medications

The investigator or qualified designee will record medication, if any, taken by the participant during the trial. In addition, new medication started during the Second Course should be recorded. All medications related to reportable SAEs and ECIs should be recorded as defined in Section 7.2.

6.1.1.6 Disease Details and Treatments

6.1.1.6.1 Disease Details

The investigator or qualified designee will obtain prior and current details regarding disease status.

6.1.1.6.2 Prior Treatment Details

The investigator or qualified designee will review all prior cancer treatments including systemic treatments, radiation and surgeries.

6.1.1.6.3 Subsequent Anti-Cancer Therapy Status

The investigator or qualified designee will review all new anti-neoplastic therapy initiated after the last dose of trial treatment. If a participant initiates a new anti-cancer therapy within 30 days after the last dose of trial treatment, the 30-day Safety Follow-up visit must occur before the first dose of the new therapy. Once new anti-cancer therapy has been initiated, the participant will move into survival follow-up.

6.1.1.7 Assignment of Screening Number**6.1.1.8 Assignment of Randomization Number**

Not applicable.

6.1.1.9 Trial Compliance (Medication/Diet/Activity/Other)**6.1.2 Clinical Procedures/Assessments****6.1.2.1 Adverse Event (AE) Monitoring**

The investigator or qualified designee will assess each participant to evaluate for potential new or worsening AEs as specified in the Trial Flow Chart and more frequently if clinically indicated. Adverse experiences will be graded and recorded throughout the study and during the follow-up period according to NCI CTCAE Version 5.0 (see Appendix 2). Toxicities will be characterized in terms regarding seriousness, causality, toxicity grading, and action taken with regard to trial treatment.

Please refer to section 7.2 for detailed information regarding the assessment and recording of AEs.

6.1.2.2 Full Physical Exam

The investigator or qualified designee will perform a complete physical exam during the screening period. Clinically significant abnormal findings should be recorded as medical history. A full physical exam should be performed during screening.

6.1.2.3 Directed Physical Exam

For cycles that do not require a full physical exam per the Trial Flow Chart, the investigator or qualified designee will perform a directed physical exam as clinically indicated prior to trial treatment administration.

6.1.2.4 Vital Signs

The investigator or qualified designee will take vital signs at screening, prior to the administration of each dose of trial treatment and at treatment discontinuation as specified in the Trial Flow Chart (Section 6.0). Vital signs should include temperature, pulse, respiratory rate, weight and blood pressure. Height will be measured at screening only.

6.1.2.5 Eastern Cooperative Oncology Group (ECOG) Performance Scale

The investigator or qualified designee will assess ECOG status (see Appendix 1) at screening, prior to the administration of each dose of trial treatment and discontinuation of trial treatment as specified in the Trial Flow Chart.

6.1.2.6 Tumor Imaging and Assessment of Disease

Tumor assessments will be performed by computer tomography (CT), PET/CT or Magnetic Resonance Imaging (MRI).

Tumor imaging is strongly preferred to be acquired by computed tomography (CT). For the abdomen and pelvis, contrast-enhanced magnetic resonance imaging (MRI) may be used when CT with iodinated contrast is contraindicated, or when local practice mandates it. MRI is the strongly preferred modality for imaging the brain. The same imaging technique regarding modality, ideally the same scanner, and the use of contrast should be used in a participant throughout the study to optimize the reproducibility of the assessment of existing and new tumor burden and improve the accuracy of the assessment of response or progression based on imaging.

Scans obtained prior to consenting will be allowed, as long as performed within 21 days of study initiation. CT Scans or MRI's will be repeated every 3 cycles (3 weeks cycles); that is before every fourth dose of pembrolizumab in order to assess response to therapy. Tumor imaging will only be required every 12 weeks for patients that have been on treatment for more than 1 year. Immune Response Evaluation Criteria (iRECIST) [36] will be utilized for assessment of response to therapy.

Expedited confirmation of measurable disease based on RECIST 1.1 at Screening should be used to determine participant eligibility. Confirmation that the participant's imaging shows at least 1 lesion that is appropriate for selection as a target lesion per RECIST 1.1 is highly recommended prior to participation allocation.

Participant eligibility will be determined using local assessment (Investigator assessment) based on RECIST 1.1. In addition, images (including via other modalities) that are obtained at an unscheduled time point to determine disease progression, as well as imaging obtained for other reasons, but which demonstrate radiologic progression, should also be used to determine progression.

When the Investigator identifies radiographic progression per RECIST 1.1, efforts should be made to verify radiologic PD. Treatment should continue until PD has been verified. Regardless of whether PD is verified, if the Investigator considers the participant has progressed, but elects to implement iRECIST, the Investigator will assess for confirmation of progression by iRECIST at subsequent time points.

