5.6 Participant Discontinuation Criteria

Discontinuation of study intervention does not represent withdrawal from the study.

Participants may discontinue study treatment at any time for any reason or be dropped from the study treatment at the discretion of the investigator should any untoward effect occur. In addition, a participant may be discontinued from study treatment by the investigator or the Sponsor if study treatment is inappropriate, the trial plan is violated, or for administrative and/or other safety reasons. Specific details regarding procedures to be performed at study treatment discontinuation are provided in Section 7.1.4 – Other Procedures.

A participant must be discontinued from study treatment but continue to be monitored in the study for any of the following reasons:

- The participant or participant's legally acceptable representative requests to discontinue study treatment
- Confirmed radiographic disease progression outlined in Section 7.1.2.6
- Any progression or recurrence of any malignancy, or any occurrence of another malignancy that requires active treatment
- Unacceptable adverse experiences as described in Section 5.2.2.
- The participant has a medical condition or personal circumstance which, in the opinion of the investigator and/or sponsor, placed the participant at unnecessary risk from continued administration of study treatment.
- The participant has a confirmed positive serum pregnancy test
- Noncompliance with study treatment or procedure requirements
- Recurrent Grade 2 pneumonitis
- Discontinuation of treatment may be considered for participants who have attained a confirmed complete response (CR) and have been treated for at least 8 cycles (at least 24 weeks), receiving 2 cycles of the combination including 2 doses of pembrolizumab and at least 80% of the planned doses of olaparib beyond the date when the initial CR was declared. These participants may be eligible for second course treatment described in Section 5.2.3.
- The participant is lost to follow-up
- Completion of 35 treatments (approximately 2 years) with pembrolizumab

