6.1.2.6.2 Tumor Imaging During the Study

The first on-study imaging assessment should be performed at 9 weeks (± 7 days) from the date of first dose. Subsequent tumor imaging should be performed every 9 weeks (± 7 days) or more frequently if clinically indicated. After 52 weeks (± 7 days), participants who remain on treatment will have imaging performed every 12 weeks (± 7 days). Imaging timing should follow calendar days and should not be

adjusted for delays in cycle starts. Imaging should continue to be performed until disease progression is identified by the Investigator.

Objective response should be confirmed by a repeat imaging assessment. Tumor imaging to confirm PR or CR should be performed at least 4 weeks after the first indication of a response is observed. Participants will then return to regular scheduled imaging every 9 weeks, starting with the next scheduled imaging time point. Participants who receive additional imaging for confirmation do not need to undergo the next scheduled tumor imaging if it is less than 4 weeks later; tumor imaging may resume at the subsequent scheduled imaging time point.

Per iRECIST (Section 7.1.2.6.6), disease progression should be confirmed by the site 4 to 8 weeks after first radiologic evidence of PD in clinically stable participants. Participants who have unconfirmed disease progression may continue on treatment at the discretion of the investigator until progression is confirmed by the site provided they have met the conditions detailed in Section 7.1.2.6.6. Participants who receive confirmatory imaging do not need to undergo the next scheduled tumor imaging if it is less than 4 weeks later; tumor imaging may resume at the 1.2.6.6.subsequent scheduled imaging time point, if clinically stable. Participants who have confirmed disease progression by iRECIST, as assessed by the site, will discontinue study treatment. Exceptions are detailed in Section 7.

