6.1.2.6.5 RECIST 1.1 Assessment of Disease

RECIST 1.1 will be used as the primary measure for assessment of tumor response, date of disease progression, and as a basis for all protocol guidelines related to disease status (eg, discontinuation of study treatment). Although RECIST 1.1 references a maximum of 5 target lesions in total and 2 per organ, the Sponsor allows a maximum of 10 target lesions in total and 5 per organ, if clinically relevant to enable a broader sampling of tumor burden.

6.1.2.6.6 iRECIST Assessment of Disease

iRECIST is based on RECIST 1.1 but adapted to account for the unique tumor response seen with immunotherapeutic drugs. When clinically stable, participants should not be discontinued until progression is confirmed by the Investigator, working with local radiology, according to the rules below. This allowance to continue treatment despite initial radiologic PD takes into account the observation that some participants can have a transient tumor flare in the first few months after the start of immunotherapy, and then experience subsequent disease response.

[figure not shown]
A description of the adaptations and iRECIST process is provided in Appendix 4, with additional detail in the iRECIST publication [Seymour et al., 2017]. iRECIST will be used by the Investigator to assess tumor response and progression, and make treatment decisions.

Table 8 Imaging and Treatment after First Radiologic Evidence of Progressive Disease

	Clinically Stable		Clinically Unstable	
	Imaging	Treatment	Imaging	Treatment
First radiologic evidence of PD by RECIST 1.1	Repeat imaging at 4 to 8 weeks to confirm PD	May continue study treatment at the Investigator's discretion while awaiting confirmatory tumor imaging by site by iRECIST	Repeat imaging at 4 to 8 weeks to confirm PD per Investigator's discretion only	Discontinue treatment
Repeat tumor imaging confirms PD (iCPD) by iRECIST per Investigator assessment	No additional imaging required	Discontinue treatment (exception is possible upon consultation with Sponsor)	No additional imaging required.	Not applicable
Repeat tumor imaging shows iUPD by iRECIST per Investigator assessment	Repeat imaging at 4 to 8 weeks to confirm PD. May occur at next regularly scheduled imaging visit	Continue study treatment at the Investigator's discretion	Repeat imaging at 4 to 8 weeks to confirm PD per Investigator's discretion only	Discontinue treatment

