Appendix 4: Description of the iRECIST Process for Assessment of Disease Progression

Assessment at Screening and Prior to RECIST 1.1 Progression

Until radiographic progression based on RECIST 1.1, there is no distinct iRECIST assessment.

Assessment and Decision at RECIST 1.1 Progression

In participants who show evidence of radiological PD by RECIST 1.1 the Investigator will decide whether to continue a participant on study treatment until repeat imaging is obtained (using iRECIST for participant management (see Table 5 and Figures 1 and 3). This decision by the Investigator should be based on the participant's overall clinical condition.

Clinical stability is defined as the following:

- Absence of symptoms and signs indicating clinically significant progression of disease
- No decline in ECOG performance status
- No requirements for intensified management, including increased analgesia, radiation, or other palliative care

Any participant deemed clinically unstable should be discontinued from study treatment at site-assessed first radiologic evidence of PD and is not required to have repeat tumor imaging for confirmation of PD by iRECIST.

If the Investigator decides to continue treatment, the participant may continue to receive study treatment and the tumor assessment should be repeated 4 to 8 weeks later to confirm PD by iRECIST, per Investigator assessment. I

Tumor flare may manifest as any factor causing radiographic progression per RECIST 1.1, including:

- Increase in the sum of diameters of target lesion(s) identified at baseline to $\geq 20\%$ and ≥ 5 mm from nadir
 - Please note: the iRECIST publication uses the terminology “sum of measurements”, but “sum of diameters” will be used in this protocol, consistent with the original RECIST 1.1 terminology.
- Unequivocal progression of non-target lesion(s) identified at baseline
- Development of new lesion(s)

iRECIST defines new response categories, including iUPD (unconfirmed progressive disease) and iCPD (confirmed progressive disease). For purposes of iRECIST assessment, the first visit showing progression according to RECIST 1.1 will be assigned a visit (overall) response of iUPD, regardless of which factors caused the progression.

At this visit, target and non-target lesions identified at baseline by RECIST 1.1 will be assessed as usual.

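### Section 6.1.2.6 continues treatment until progression is verified, with no clinical-stability condition, whereas Table 8 and Appendix 4 stop clinically unstable participants at first radiologic progression

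*Combined protocol and SAP*

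**What the plan says.** **Section 6.1.2.6**, in its introductory text, covers the moment at which the investigator identifies radiographic progression by RECIST 1.1. It asks for efforts to verify the progression and then says: "Treatment should continue until PD has been verified". It mentions neither clinical stability nor investigator discretion. The sentence that follows treats iRECIST confirmation as something that may happen whether or not verification does.

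**Section 6.1.2.6.2** says that "disease progression should be confirmed by the site 4 to 8 weeks after first radiologic evidence of PD in clinically stable participants", and leaves continuation before confirmation to the investigator.

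**Section 6.1.2.6.6** opens with "When clinically stable, participants should not be discontinued until progression is confirmed by the Investigator". Its Table 8 then splits the action by stability. At first radiologic progression, a stable participant may continue at the investigator's discretion. For an unstable participant the imaging cell reads "Repeat imaging at 4 to 8 weeks to confirm PD per Investigator's discretion only", and the treatment cell beside it says to discontinue.

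**Appendix 4** defines clinical stability and states: "Any participant deemed clinically unstable should be discontinued from study treatment at site-assessed first radiologic evidence of PD". It adds that such a participant does not need a repeat scan.

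**Section 5.6** lists reasons for mandatory discontinuation. They include a condition that "placed the participant at unnecessary risk from continued administration of study treatment", "Any progression or recurrence of any malignancy", and "Confirmed radiographic disease progression outlined in Section 7.1.2.6".

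**Section 2.0** permits treatment past initial iRECIST progression only case by case, where the physician documents clinical benefit and tolerance.

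**The concern.** A site with a deteriorating patient and a first scan showing progression finds two opposite dosing instructions. The introductory text says to keep treating until something called verification has happened. The table and the appendix say to stop now. No text states which prevails, and 6.1.2.6 and Appendix 4 both use *should*, so strength of wording does not rank them.

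What is at stake is the conduct of treatment and patient safety: two active drugs given to a patient whose disease and condition are both worsening. Section 2.1 describes the trial as multi-center, so sites could also apply the rule differently.

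**Working it through.** The plan gives no figure on this point, so there is nothing to recompute. The check compares the texts.

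**Step 1. Unstable participant, first site-assessed progression.**
- Section 6.1.2.6: continue until verified.
- Table 8, first row, unstable column: discontinue; repeat imaging is optional.
- Appendix 4: discontinue; no repeat imaging required.

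One sentence conflicts directly with two places. Section 6.1.2.6.2 supports those two by inference, because it confines confirmation to clinically stable participants.

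**Step 2. Does any meaning of *verified* reconcile them?** The term is not defined for on-treatment progression. Three places point towards central review:
- Section 5.2.3 refers to centrally verified progression in the Second Course criteria.
- Section 6.1.2.6.1 sends screening images to a central imaging vendor.
- Section 7.2 dates progression for PFS by central review.

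None of these describes a step, a responsible party or a time limit for verifying progression during treatment. Two readings can be tried:
- *Central or second read of the same scan.* Appendix 4 sets the stop at the site's own first assessment, before any such read could be returned. The conflict remains.
- *iRECIST confirmation.* This would mean waiting 4 to 8 weeks for the repeat scan that Appendix 4 does not require of unstable participants. The conflict remains. The reading is also strained, because 6.1.2.6 itself keeps verification and iRECIST confirmation apart.

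**Step 3. Stable participant, first progression.** The conflict here is one of degree:
- Section 6.1.2.6: should continue.
- Opening of 6.1.2.6.6: should not be discontinued.
- Table 8 and 6.1.2.6.2: may continue, at the investigator's discretion.
- Section 2.0: case by case, with documented benefit and tolerance. I read this as covering the wait for confirmation.
- Section 5.6: one bullet requires confirmed progression, while another, read literally, stops treatment at any progression.

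A repair confined to the unstable case would leave these differences standing.

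**Step 4. Cross-references to this rule.**
- Section 5.6 cites 7.1.2.6: 1.
- Section 6.1.2.6.2 cites 7.1.2.6.6 twice, and Section 7 for the exceptions: 3.
- Appendix 4 cites Table 5, which is the infusion-reaction table: 1.

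Total: 1 + 3 + 1 = 5. Section 7 is now the statistical analysis plan and has no such subsections. These are renumbering slips and add no weight to the point.

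**The case against.** The strongest reply is that the protocol already contains the right rule. The sentence is introductory, and the subsections beneath it, with Appendix 4, give the operative instructions, split by stability and consistent on the unstable case. Section 2.0 restricts treatment past progression, and Section 5.6 says *must* where 6.1.2.6 says *should*. An experienced site would probably follow the specific text. On this view the matter is a drafting clean-up.

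Much of that stands, and it is why the point is rated no higher than minor to moderate. It does not dispose of the point. The texts relied on contradict the sentence without reconciling it. The bullet on any progression is also an awkward safeguard: if it covers cervical progression, it forbids the continuation that Table 8 allows for stable participants. Section 5.8 counts clinical deterioration after two doses as progression, but that is a counting rule and gives no dosing instruction.

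A reader might infer that unstable patients will in fact be dosed for weeks past progression, or indefinitely because verification has no deadline. The documents do not support that. The specific rules and the mandatory list in 5.6 point the other way, and no rate of clinical instability at first progression is given from which exposure could be estimated.

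**Conclusion.** The sentence in 6.1.2.6 is wrong as written and should be replaced. The error is minor to moderate: one unconditional instruction against two direct contrary ones, on a safety-relevant dosing decision, with other text limiting the likely harm. The number of patients affected and the length of any extra dosing cannot be derived.

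A reader might also infer that the primary result is compromised. It is not on this ground: the sample size of 48 and the rule of 10 or more responses in Section 7.2 do not depend on this sentence.

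The conclusion rests on a literal reading of 6.1.2.6 and on the absence of any stated order of precedence. It does not depend on which meaning of *verified* was intended.

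**What to change.** 1. Replace the sentence in 6.1.2.6 with: *Clinically unstable participants discontinue at first site-assessed radiologic PD; clinically stable participants may continue at the Investigator's discretion, with clinical benefit and tolerance documented (Section 2.0), until PD is confirmed per iRECIST (Table 8).*
2. Delete the remaining verification wording in that paragraph. If the sponsor does want a separate step, name who performs it and limit it to clinically stable participants.
3. Change the opening of 6.1.2.6.6 from a statement that stable participants should not be discontinued to the permissive wording of Table 8.
4. State in 5.6 that the bullet on any progression does not override the iRECIST confirmation rule for clinically stable participants.
5. As editorial clean-up, correct the five pointers: in 5.6, 7.1.2.6 becomes 6.1.2.6; in 6.1.2.6.2, both citations of 7.1.2.6.6 become 6.1.2.6.6, and Section 7 becomes Table 8 and Appendix 4; in Appendix 4, Table 5 becomes Table 8.

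The cost is one replaced sentence, one sponsor decision on verification, two small wording alignments and five cross-references in the next amendment. No new procedure or data is needed unless a separate verification step is kept.
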